5.12.2 Non-Serious Adverse Event Reporting Requirements

All AEs and SAEs will be reported on the AE page(s) of the CRF.

5.12.3 Sponsor Reporting Requirements to Regulatory Authorities

AE reporting, including suspected serious unexpected adverse reactions (SUSARs), will be carried out in accordance with applicable local regulations.

Data Collection, Management and Analysis

6.1 **Source Data**

Source documents (including all demographic and medical information, CRFs, and a copy of the signed ICF indicating the study number and title) for each patient in the study will be maintained by the Investigator (generally in the patient's files), and all information in the CRFs must be traceable to the source documents.

All data should be recorded directly into the patient's medical record as source data. It will be confirmed at the study initiation monitoring visit which documents will be considered as source data for each site. These will be documented and reviewed by the monitor at each monitoring visit.

Source documents must be available to document the existence of the patient and substantiate the integrity of study data collected.

6.2 Data Collection, Management and Reporting

Procedures for data management (i.e., entry, storage, etc.) are outlined in the study's Data Management Plan.

6.2.1 Case Report Forms/Electronic Data Record

As used in this protocol, the term CRF should be understood to refer to either a paper form or an electronic data record or both, depending on the data collection method used in this study.

A CRF is required and should be completed for each included patient. The completed original CRFs are the sole property of Kazia Therapeutics Limited and should not be made available in any form to third parties, except for authorized representatives of Kazia Therapeutics Limited or appropriate regulatory authorities, without written permission from Kazia Therapeutics Limited.

The Investigator has ultimate responsibility for the collection and reporting of all clinical, safety and laboratory data entered on the CRFs and any other data collection forms (source documents) and ensuring that they are accurate, authentic / original, attributable, complete, consistent, legible, timely (contemporaneous), enduring and available when required. The CRFs must be signed by the Investigator or by an authorized staff member to attest that the data contained on the CRFs is true. Any corrections to entries made in the CRFs, source documents must be dated, initialed and explained (if necessary) and should not obscure the original entry. Data transcribed on the CRF. which are derived from source documents, should be consistent with the source documents or the discrepancies should be explained.

In most cases, the source documents are the hospital's or the physician's patient chart. In these cases, data collected on the CRFs must match the data in those charts.

In some cases, the CRF, or part of the CRF, may also serve as source documents. In these cases, a document should be available at the Investigator's site as well as at Kazia Therapeutics Limited and clearly identify those data that will be recorded in the CRF, and for which the CRF will stand as the source document.

6.2.2 **Record Retention**

To enable evaluations and/or audits from regulatory authorities or Kazia Therapeutics Limited, the Investigator agrees to keep records, including the identity of all participating patients (sufficient

Version: Amendment 4 Date: 31 Mar 2020

information to link records, e.g., CRFs and hospital records), all original signed informed consent documents, copies of all CRFs, safety reporting forms, source documents, and detailed records of treatment disposition, and adequate documentation of relevant correspondence (e.g., letters, meeting minutes, telephone calls reports). The records should be retained by the Investigator according to

International Council on Harmonization (ICH), local regulations, or as specified in the Clinical Study

Protocol Number: NVGN-0084-201

IND Number: 112.608

Agreement, whichever is longer.

If the Investigator becomes unable for any reason to continue to retain study records for the required period (e.g., retirement, relocation), Kazia Therapeutics Limited should be prospectively notified. The study records must be transferred to a designee acceptable to Kazia Therapeutics Limited, such as another Investigator, another institution, or to an independent third party arranged by Kazia Therapeutics Limited. Investigator records must be kept for a minimum of 15 years after completion or discontinuation of the study or for longer if required by applicable local regulations.

The Investigator must obtain Kazia Therapeutics Limited's written permission before disposing of any records, even if retention requirements have been met.

6.3 Statistical Methods

A Statistical Analysis Plan (SAP) will be prepared as a separate document and will include a more technical and detailed description (including the handling of missing data, transformations and other data handling procedures as well as templates for Tables, Listings, and Figures) of the planned statistical summaries. The SAP is a higher level document that the relevant statistical-related text following. The SAP will be finalized before initiating any statistical analysis. Tabulation of summary statistics and data analysis will be performed using SAS®.

6.3.1 Analysis Populations

The following analysis populations are defined:

- The Intent -to-Treat (ITT) population includes all randomized patients; ITT analyses will be conducted on the basis of the arm assigned at randomization
- The Modified Intent-to-Treat (mITT) population includes allI eligible patients who received at least 1 dose of GDC-0084 and have evaluable post-baseline tumor response data; mITT analyses will be conducted on the basis of the treatment assigned at randomization;
- Safety population (SAF): All eligible patients who received at least 1 dose of GDC 0084 will be included in the safety population. Safety analyses will be conducted on the basis of initial received treatment;
- PK population: All eligible patients in the safety population who have an adequate concentration vs. time profile to determine PK parameters
- A Per-Protocol (PP) subset will also be used to analyze endpoints of clinical benefit and will be based on study drug exposure (compliance and/or time on study drug) and major protocol deviations. The criteria for inclusion in the PP subset will be finalized and documented prior to database lock.

6.3.2 Timing of Analyses

Regular cohort safety reviews will be performed as described above during Stage 1 to support dose-escalation and if necessary, de-escalation decisions.

A final analysis will be performed when all patients discontinue treatment and complete their EoT visit. Supplemental analyses may be performed at the completion of the study but will be considered exploratory.

6.3.3 General Considerations

Data from Stage 1 and Stage 2 may be summarized separately. For Stage 1 assessment, summaries will be presented by dose level and overall. For Stage 2, summaries will be presented by treatment arm (fed versus fasting) and overall. Selected safety parameters may be summarized using pooled data from the selected dose level in Stage 1 and fasted patients in Stage 2.

Version: Amendment 4 Date: 31 Mar 2020

Protocol Number: NVGN-0084-201

IND Number: 112,608

There may be a statistical comparison of C_{max}/AUC between fasted and fed patient data in Stage 2. Descriptive statistics (N, mean, standard deviation, median, minimum, and maximum) will be presented for continuous variables. Geometric means and geometric coefficient of variation will also be presented for PK data. Frequency distributions (counts and associated percentages) will be presented for categorical variables. Median, 25th and 75th percentiles and confidence intervals (CIs) will be presented for time-to-event data. Unless specified otherwise, CIs will be presented as 95%

The study is descriptive in nature and is not powered for a confirmatory statistical goal or objective. However, comparisons of treatment arms may be performed in Stage 2. Formal hypothesis testing will not be done, and no adjustment for multiple comparisons will be used.

Individual patient data listings will be provided to support summary tables.

The effects of noncompliance, treatment discontinuations, premature study withdrawals, subsequent therapies, and covariates will be assessed to determine the impact on the general applicability of results from this study.

6.3.4 **Analysis of Clinical Benefit**

Analyses of tumor-related endpoints will include all evaluable data collected until initiation of subsequent anti-cancer therapy. Sensitivity analyses may be performed excluding data collected after the End of Treatment Visit.

Requirements for PD confirmation and any impact on the calculations for analysis (i.e., PFS, TTP. duration or stable disease, etc.) and associated sensitivity analyses will be described in the SAP.

For Stage 2 tumor-related endpoints, the responses assigned by the blinded central review will be used as the primary measure for analysis, and the responses assigned by the Investigator will be used as supportive measures for analysis.

PFS is defined as the time in months from start date and/or date of disease diagnosis until disease progression or death due to any cause. Patients without disease progression or death will be censored at the last evaluable radiographic assessment. Patients with no post-dose radiographic assessment will be censored at their start date (Day 1). The primary analysis of PFS will be conducted in the SAF for Stage 1 and the mITT for Stage 2. Analyses of PFS may be repeated in the PP.

The Kaplan-Meier method will be used to describe and present PFS. Median PFS will be presented with 95% CI, 25th and 75th percentiles and minimum and maximum values. Kaplan-Meier estimates of PFS at 6, 9, and 12 months will also be presented with 95% CIs. PFS will also be displayed graphically using Kaplan-Meier estimates.

For Stage 2, differences between treatment arms will be tested using a two-sided log rank test. Stratified hazard ratio (HR) estimates of the treatment comparisons with associated 95% CIs will be estimated from a Cox regression model.

OS is defined as the time in months from start date and/or disease diagnosis until death due to any cause. Patients who are alive at the time of analysis will be censored at the date last known to be alive. The primary analysis of PFS will be conducted in the SAF for Stage 1 and the ITT for Stage 2. Analyses of OS may be repeated in the mITT and/or PP.

TTP is defined as the time in months from start date and/or until disease progression . Patients without disease progression will be censored at the last evaluable radiographic assessment. Patients with no post-dose radiographic assessment will be censored at their start date (Day 1).

Analyses of OS and TTP will be performed using the same methods as described for PFS.

Post-hoc stratification/analysis factors may include disease progression (post-surgery at time of baseline visit) and baseline KPS.

Version: Amendment 4 Date: 31 Mar 2020

Protocol Number: NVGN-0084-201

IND Number: 112.608

The exploratory endpoint DCR is defined as the proportion of patients achieving a confirmed BOR of CR, PR or SD according to a) RANO criteria and b) modified RANO criteria. BOR is defined as the best response recorded from first dose (Stage 1) or randomization (Stage 2) until progressive disease , death, withdrawal of consent or end of study, whichever occurs first. To be assigned a status of CR, PR or SD, the response must be confirmed by repeat assessments that should be performed no less than 28 days after the criteria for response are first met, i.e., patients need to have two consecutive assessments of CR, PR or SD. To be assigned a BOR of SD patients must have a minimum duration of SD of at least 6 weeks.

The number and proportion of responders and non-responders based on objective response rate and DCR will be presented with 95% Clopper-Pearson Cls. Further, objective response rate and DCR will be compared between treatment arms using Fisher's exact test. The difference in the proportion of responders and corresponding 95% CI (based on the Hauck-Anderson approach) will also be displayed.

Analyses of PFS will be repeated using modified RANO criteria.

Additional exploratory analyses of the data will be conducted as deemed appropriate.

6.3.5 **Safety Analysis**

All safety analyses will be conducted in the safety population.

AEs will be coded according to the Medical Dictionary for Regulatory Activities (MedDRA). The severity of AEs will be graded according to the United States NCI CTCAE, version 4.03.

TEAEs are defined as any AE occurring or worsening on/after the first study drug dose and within 28 days after the last dose date. TEAEs leading to study drug discontinuation, TEAEs leading to dose reduction/interruption, TEAEs related to study drug, SAEs, TEAEs leading to study drug discontinuation, and TEAEs with an outcome of death will be summarized by system organ class, and preferred term. Disease progression and death will be reported as part of the study endpoints and not as AEs or SAEs. A summary of TEAEs of NCI CTCAE Grade 3 or higher, as well as the most frequent TEAEs (preferred terms) by grade, and TEAEs by relationship to study treatment, will be provided. Additionally, a summary will be done for AEs using the worst grade of the event.

Values and changes from baseline (last value obtained prior to first dose) in clinical laboratory results will be summarized by visit. Clinical laboratory values will be graded according to the NCI CTCAE 4.03, for applicable tests. Shifts in CTC grades from baseline grade will be summarized. The number and percentage of patients with treatment-emergent Grade 3/4 clinical laboratory abnormalities will also be presented. The number and percentage of patients with abnormally high glucose values (hyperglycemia) or abnormally low platelet values (thrombocytopenia) will be summarized overall and by CTC grade (since these are DLT criteria).

KPS data will be summarized categorically (number and percentage of patients with each score at each visit).

Values and changes from baseline in vital signs will be summarized by visit.

Values and changes from baseline in ECG, parameters will be summarized by visit. The number and percentage of patients with an increase of QTc to ≥ 500 msec or a change from baseline of at least 60 msec will be presented overall and by visit. The number and percentage of patients with ECG abnormalities at each visit will also be presented.

Values and changes from baseline in LVEF will be summarized by visit. The number and percentage of patients with a drop in LVEF to ≤ 45% will be presented. Troponin T and B-type natriuretic peptide values will be listed.

Changes in corticosteroid use will be summarized. Further details on corticosteroid use will be defined in the SAP.

Concomitant medications are defined as any medications taken on/after the first study drug dose (including those started prior to first dose and ongoing at time of first dose) and within 28 days after

Version: Amendment 4 Date: 31 Mar 2020

Date. 31 Wai 2020

the last dose date. Concomitant medication use will be summarized. Any medications started and stopped prior to first dose or started after last dose + 28 days will be listed but not summarized.

Protocol Number: NVGN-0084-201

IND Number: 112.608

Treatment exposure will be summarized. Patient diaries will be used to assess compliance.

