4.5 Endpoints

4.5.1 **Primary Endpoint**

The primary endpoint of this study is safety-related and is the occurrence of DLTs during the study.

Protocol Number: NVGN-0084-201

Secondary Endpoints 4.5.2

Secondary endpoints are related to both, safety and clinical benefit as listed below.

Secondary Safety Endpoints:

- Treatment-emergent AEs (TEAEs), Grade 3-5 TEAEs, serious adverse events (SAEs), fatal AEs, and TEAEs leading to GDC 0084 discontinuation or study withdrawal;
- Treatment-emergent Grade 3/4 clinical laboratory abnormalities;
- Changes and shifts from baseline in clinical laboratory, vital signs, and ECG parameters;
- Change from baseline in corticosteroid use;
- Change from baseline in LVEF;
- Change from baseline in KPS;
- Concomitant medication use;
- Adherence to the dosing regimen.

Secondary Endpoints of Clinical Benefit:

- PFS measured from first dose in the dose-escalation portion (Stage 1) or from randomization in the cohort expansion portion of the study (Stage 2) to disease progression (RANO criteria) or death due to any cause:
- OS measured from first dose in the dose-escalation portion (Stage 1) or from randomization in the cohort expansion portion of the study (Stage 2) to death due to any cause;
- TTP measured from first dose in the dose-escalation portion (Stage 1) or from randomization in the cohort expansion portion of the study (Stage 2) to date of earliest disease progression according to RANO criteria.

4.5.3 **Exploratory Endpoints**

Exploratory endpoints in this study are:

- PFS measured from first dose in the dose-escalation portion (Stage 1) or from randomization in the cohort expansion portion of the study (Stage 2) to disease progression (modified RANO criteria) or death due to any cause:
- PK parameters including area under the curve from time 0 to last measurable time point (AUC_{0-last}) and/or area under the curve from time 0 to infinity (AUC_{0-inf}), maximum concentration (C_{max}), minimum concentration (C_{min}), time to reach C_{max} (T_{max}), t_{1/2}, apparent total clearance of the drug from plasma after oral administration (CL/F), and accumulation ratio for C_{max} and AUC (fed and fasted);
- Change in FDG-PET uptake in tumor and normal brain tissue (defined as normal brain tissue with similar cell type to tissue surrounding tumor) in response to GDC-0084 in patients with measurable disease:

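### Section 6.3.4 lets PFS and OS be timed from diagnosis, against the first-dose/randomization origin in 4.5.2; used, that option inflates Kaplan-Meier medians and 6-, 9- and 12-month rates

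*Combined protocol and SAP*

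**What the plan says.** The endpoint definitions in section 4.5.2, repeated in the synopsis, give one origin for each stage: "PFS measured from first dose in the dose-escalation portion (Stage 1) or from randomization in the cohort expansion portion of the study (Stage 2"). OS and TTP have the same origin there.

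Section 6.3.4 defines the same endpoints again for analysis:

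- PFS: "PFS is defined as the time in months from start date and/or date of disease diagnosis until disease progression" (or death).
- OS: "OS is defined as the time in months from start date and/or disease diagnosis until death due to any cause".
- TTP: "TTP is defined as the time in months from start date and/or until disease progression". The second origin is missing and the sentence is unfinished.

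It does not say when each origin applies, or which estimate is primary if both are reported. Medians and Kaplan-Meier estimates at 6, 9 and 12 months are planned for PFS, and the same methods are carried over to OS and TTP. No delayed-entry adjustment is mentioned.

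Other sentences in 6.3.4 assume the entry-based clock. The censoring rule is "Patients with no post-dose radiographic assessment will be censored at their start date (Day 1"), and the response endpoint follows 4.5.2: "BOR is defined as the best response recorded from first dose (Stage 1) or randomization (Stage 2) until progressive disease".

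**The concern.** The two sections give different time origins for the same secondary endpoints. On 6.3.4 as written, two analysts could time the same patients differently and report different medians and landmark rates.

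The start-date option agrees with 4.5.2 and does no harm. The diagnosis option does. To be enrolled, a patient must have survived surgery and most of chemoradiation, so the interval from diagnosis to entry contains no deaths by construction. An unadjusted Kaplan-Meier curve credits that interval as survival. For PFS the interval is event-free only if progression before entry is not counted, and the text leaves this open. It even lists progression at baseline as a possible factor: "Post-hoc stratification/analysis factors may include disease progression (post-surgery at time of baseline visit").

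The Day 1 censoring rule also changes meaning. A patient with no post-dose scan contributes zero follow-up on the start-date clock and the whole lead time on the diagnosis clock.

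What is at stake is the absolute PFS and OS figures and any reading of them beside historical values. They could look longer without any drug effect.

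**Working it through.** **The plan's own figure.** The protocol states no target median, landmark rate, event count or power that depends on the time origin, so there is nothing to reproduce. What follows illustrates the diagnosis option.

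**Inputs**

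- Surgery to start of radiation: up to 6 weeks (4.2.1, criterion 5).
- Radiation course: 6 weeks (4.4.1), of which at least 75% must have been received (4.2.1).
- Screening: up to 28 days (4.4.2). No maximum gap after radiation is stated.
- Medians: PFS 5.3 and OS 12.7 months (3.2). Their time origin is not stated; they are used here as post-entry medians, which is an assumption.
- Further assumptions: diagnosis dated at surgery, exponential times, no drug effect, pre-entry progression not counted.

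**Lead time a** (one week = 12/52.1775 month)

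- Short: 0.75 × 6 = 4.5 weeks = 1.03 months.
- Long: 6 + 6 + 4 = 16 weeks = 3.68 months. This is not an upper limit.

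**Effect.** A common lead time a shifts the curve to the right: S_dx(t) = exp(−ln 2 × (t − a)/m), and the median becomes m + a.

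Example, PFS at 6 months with m = 5.3:

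- From entry: exp(−0.693 × 6/5.3) = 0.456.
- a = 1.03: exp(−0.693 × 4.97/5.3) = 0.522.
- a = 3.68: exp(−0.693 × 2.32/5.3) = 0.738.

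| Quantity | From entry | From diagnosis, a = 1.03 | From diagnosis, a = 3.68 |
|---|---|---|---|
| PFS, 6 months | 45.6% | 52.2% | 73.8% |
| PFS, 9 months | 30.8% | 35.3% | 49.9% |
| PFS, 12 months | 20.8% | 23.8% | 33.7% |
| Median PFS (months) | 5.3 | 6.3 | 9.0 |
| OS, 12 months | 51.9% | 55.0% | 63.5% |
| Median OS (months) | 12.7 | 13.7 | 16.4 |

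**Sensitivity**

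- Weibull times with median 5.3, S(t) = exp(−ln 2 × (t/5.3)^k). With k = 0.8, 6-month PFS moves from 46.5% to 52–70%. With k = 1.5, it moves from 43.4% to 53–82%.
- Other PFS medians, exponential. With m = 4, 6-month PFS moves from 35.4% to 42.3–66.9%. With m = 8, it moves from 59.5% to 65.0–81.8%.
- Variable lead times: 2,000 simulated trials of 32 patients, lead time uniform on 4.5–16 weeks, censoring uniform on 6–24 months (both assumed). On average 6-month PFS moved from 45% to 62%, median PFS from 5.2 to 7.6 months, median OS from 12.8 to 15.2 months and 12-month OS from 52% to 59%. At least one estimate came out lower in 6% (PFS) and 10% (OS) of trials.

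**Is it bias, or only a different clock?** To separate the two, 400,000 exponential times with median 5.3 were generated from diagnosis itself, with entry uniform on 1.03–3.68 months, and only patients event-free at entry were kept. The true 6-month value from diagnosis is 45.6%; ordinary Kaplan-Meier gave about 62%. Left-truncated Kaplan-Meier, conditional on being event-free at 1.13 months, gave about 53%, against a true conditional value of exp(−0.693 × (6 − 1.13)/5.3) = 52.9%. Left truncation removes the bias, but what it then estimates is conditional.

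**The case against.** **A separate SAP is promised and will outrank this text.** Section 6.3 says so and adds: "The SAP will be finalized before initiating any statistical analysis". Its list of contents is not exhaustive, so the SAP may settle the origin. This stands as a possibility, and the two-analyst problem arises only if the SAP is silent. But that SAP is not among the documents, the time origin is not among the items section 6.3 names for it, and two protocol sections would still disagree.

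**The rest of the protocol points to one origin, and the wording could mean that both clocks will be reported.** This also has force: diagnosis is the outlier. Two clearly labelled curves would mislead less than a substitution, but the text would still have to say which is primary and how pre-entry time is handled.

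**The two clocks measure different things, so the table mixes a change of definition with late-entry bias.** That is true of the table. The simulation isolates the bias, and it is large.

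**The size rests on assumptions, and sampling error is wide.** Agreed. A simple 95% interval around 45.6% with 20 patients is ±1.96 × √(0.456 × 0.544/20) = ±22 points, against a low-end shift of about 7. The short lead time is also a minimum, since it allows no gap before radiation or after it. Wide intervals do not remove a systematic shift, however.

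**Start date is not defined by stage.** This is a small gap. Table 1 (footnotes) and section 4.6.3 place randomization and first intake at the same Week 1 visit, so the practical difference is slight, but a short definition would close it.

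**Conclusion.** The concern holds. Section 6.3.4 contradicts 4.5.2 and the synopsis on the origin for PFS and OS, fits poorly with its own censoring and response rules, and leaves the TTP sentence incomplete.

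If the diagnosis option is used with ordinary Kaplan-Meier, absolute PFS and OS are overstated on average. The direction follows from the entry criteria, given for PFS that pre-entry progression is not counted. The size depends on the assumed lead time, medians and distribution; the ranges in the table are illustrations, not predictions.

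The consequences are limited. These are secondary endpoints in a descriptive study. A common lead time leaves the log-rank ranks unchanged, and randomization balances lead times in expectation, so the fed/fasted comparison is not systematically biased. No power figure or decision rule changes. It should be fixed before analysis.

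**What to change.** In section 6.3.4:

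1. In the PFS and OS sentences, replace the start-date-or-diagnosis wording with the 4.5.2 origin: first dose for Stage 1, randomization for Stage 2.
2. Complete the TTP sentence with the same origin.
3. Define the start date by stage so that the Day 1 censoring rule uses the same clock.

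Repeat the origin in the SAP. If a from-diagnosis estimate is wanted, label it supportive, left-truncate it at first dose or randomization, and state whether progression before entry counts as a PFS event.

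The cost is a few sentences in 6.3.4 and the matching SAP text, with no new data. Reported times may be shorter than under the diagnosis clock. A left-truncated curve with about 20 patients will be unstable early on because few are at risk; it is optional.
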